subarachnoid haemorrhage other or unspecified and they subsequently died within 30 days (based on the very low rate of mortality from non-aneurysmal SAH) and did not have any additional codes for trauma indicating a non-aneurysmal event.

Data collection - other considerations - central HES ONS data

Last follow-up for each patient will be set as the time at which the HES search was performed, or the patient was unregistered with a GP in the UK or date of death, or the aneurysm was treated, whichever is earliest.

Additionally, we will record

- 1. race
- 2. I10 essential (primary) hypertension
- 3. Z72.0 tobacco use
- 4. F17.2 tobacco dependence

And use these to complete any missing baseline data. Where baseline data and HES conflict, the baseline data will be used. Where neither is available, after assessment for any bias (missing completely at random MCAR, missing at random MAR, missing not at random MNAR) multiple imputation will be used.

Statistical analysis - Aim 1 - PHASES validation

The PHASES study provides the coefficients from their Cox regression model and baseline survival at 5 years that allows the absolute 5-year risk of rupture, to be calculated for all patients who are not censored before 5 years, using age, whether the patients has hypertension, history of SAH, size of aneurysm (3 categories) and location of aneurysm. The time to censoring will be calculated (death or date of HES search or date unregistered from GP practice whichever is first) to ensure 5 years of follow up if rupture has not occurred. Discrimination will be assessed using Harrell's C-index of concordance and Royston and Sauerbrei's D statistic. Calibration will be assessed at the 5 year time point using the method in Royston (2014). These will be used to calculate the number of SAH events per 5 years for each PHASES score (0 to 12+) and expressed as a percentage with 95% confidence interval to compare to the PHASES estimates.

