There are multiple potential causes leading to underestimates of rupture risk. The magnitude of these will be estimated and corrected for. In view that all SAH events will be verified in clinical notes it is not expected that there will be any significant overestimation and consequently correction. Events may be missed due to migration. Any patients noted at time of baseline data collection to have emigrated will have this recorded and this will be used for censoring. Additionally, HES data will reveal any patients who have unregistered with their GP for emigration which will be used as a censoring event. Unfortunately, it is anticipated that not all patients will unregister on departure from the UK and therefore the observed emigration rate (that from the baseline data collection and HES data) will be subtracted from average national migration figures and this applied to the data.

Events may be missed due to miscoding. Aneurysmal SAH miscoded as:

1. Cerebral infarction (63.0-63.9 & I64.X)

Will be identified at one or more test sites by review of clinical notes to estimate any under-estimates due to miscoding and these estimates applied to the whole cohort.

In the event there are high rates of failed verification for the codes:

- 1. Intracerebral haemorrhage (including intraventricular haemorrhage (I61.0-61.9)
- 2. Subarachnoid haemorrhage (other and unspecified) (I60.8-60.9)
- 3. Non-traumatic subdural haemorrhage (I62.00-I62.02)
- 4. Traumatic subarachnoid haemorrhage (S06.6X0, S06.6X9A, S06.6X9, S06.6X8A)
- 5. I46.1 sudden cardiac death R98 unattended death
- 6. R96 other sudden death cause unknown
- 7. R98 unattended death

at some centres, then error estimates may be applied to the data from centres with robust code verification.

Additionally, at baseline data collection, any subsequent SAH events observed in the local notes will be recorded with their date, or date of last follow up. The SAH events observed during this follow up period will be compared to that for the similar period using HES data (after applying the above corrections), and the total risk estimates adjusted for any differences between these to give final 5 year risk estimates.

Discrimination will be assessed with the C statistic but is expected to be poor due to low event rates and therefore will be compared to the original PHASES data. Calibration will be assessed with calibration plots and Hosmer-Lemeshow tests.

Statistical analysis – Aim 2 - Additional prognostic factors

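### Aim 1 keeps early ruptures but drops event-free patients censored before 5 years, so the observed 5-year risk per PHASES score is selected on the outcome

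*Protocol*

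**What the plan says.** Protocol section 5, statistical analysis for Aim 1, applies the published PHASES coefficients and 5-year baseline survival to obtain an absolute risk "for all patients who are not censored before 5 years". Time to censoring is computed "to ensure 5 years of follow up if rupture has not occurred". The censoring events listed there are "death or date of HES search or date unregistered from GP practice whichever is first".

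The general rule for last follow-up, earlier in section 5 under other considerations for the central HES and ONS data, is longer. It also stops the clock at treatment: "or date of death, or the aneurysm was treated, whichever is earliest".

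For performance, the Aim 1 text names Harrell's C and the D statistic, and then says "Calibration will be assessed at the 5 year time point using the method in Royston (2014"). The results are used to "calculate the number of SAH events per 5 years for each PHASES score (0 to 12" and above), as percentages with 95% confidence intervals, for comparison with the PHASES estimates. Later in the same subsection: "Calibration will be assessed with calibration plots and Hosmer-Lemeshow tests".

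The corrections planned for Aim 1 address missed events. On error in the other direction the protocol states that "it is not expected that there will be any significant overestimation and consequently correction".

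**The concern.** The 5-year requirement is waived only for patients who rupture. Take two patients diagnosed in 2018. One ruptures in 2019 and is counted. The other is intact at a search in 2021 or 2022 and is removed. Early events stay in the numerator while the comparable event-free patients leave the denominator.

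The restriction is also unnecessary. The PHASES prediction uses baseline variables only, so it can be computed for anyone whatever their follow-up. Harrell's C, the D statistic and the cited calibration method all accommodate censoring, but none can restore patients already removed.

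Aim 1 is a primary aim, and its main product is the table of observed 5-year percentages set beside the PHASES figures. A correctly calibrated PHASES score could appear to underpredict in the UK. Section 1 says 24 of 30 UK units use the score. No planned step would detect the problem. The final comparison with local notes checks whether events were captured, not who is in the analysis set.

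**Working it through.** **Inputs from the protocol**
- Planning rate (section 7.2.1): 51 ruptures in 1,692 patients over 4.1 years.
- Diagnosis window (section 7.1.1): January 2006 to December 2020.
- Follow-up (section 5, Aim 3): from months to 15 years.
- Pilot (section 7.2.1): 1,415 cases with 6,000 anticipated years of follow-up.
- Later treatment of 32% in the ISUIA conservative group (section 1), used for illustration only.

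**Assumptions, not in the protocol**
- Constant rupture hazard, independent censoring and uniform entry over 15 years.
- HES search 0.5, 1 or 2 years after the end of 2020.
- Mortality of 2% or 4% per year.

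**Step 1. Reproduce the plan.** λ = 51/(1,692 × 4.1) = 0.00735 per year. For 60 events: 60/0.00735 = 8,161 patient-years and 60/51 × 1,692 = 1,990 patients. Both match section 7.2.1.

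**Step 2. True 5-year risk.** 1 − exp(−5 × 0.00735) = 3.61%.

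**Step 3. What the Aim 1 rule estimates.** Let G(t) be the probability of still being under observation at t years. The rule keeps E, the ruptures seen within 5 years, and S, the patients followed event-free past 5 years:
- E = ∫₀⁵ λ·exp(−λt)·G(t) dt
- S = exp(−5λ)·G(5)
- estimate = E/(E + S); proportion kept = E + S

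With the search s years after the start of 2006 and mortality μ, G(t) = min(1, (s − t)/15)·exp(−μt).

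Example, s = 16 and μ = 2%: E = 0.0308, S = 0.6396, estimate = 0.0308/0.6704 = 4.60%. The ratio to truth is 1.27 and 67% are kept.

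| Mortality | Search (years after end 2020) | Estimate | Ratio to 3.61% | Kept |
|---|---|---|---|---|
| 2% | 2 | 4.43% | 1.23 | 73% |
| 2% | 0.5 | 4.66% | 1.29 | 64% |
| 4% | 2 | 4.67% | 1.29 | 66% |
| 4% | 0.5 | 4.91% | 1.36 | 58% |

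With no deaths at all, the search date alone gives 4.2-4.4% (ratio 1.17-1.23).

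**Step 4. Does keeping everyone remove the bias?** In simulations of 2 million patients with three other follow-up shapes (uniform 0-15 years; uniform with mean 4.24 years; exponential with mean 4.24 years), Kaplan-Meier on all patients gave 3.61-3.62%. The Aim 1 rule gave 4.48%, 6.06% and 6.69%.

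**Step 5. Other rupture rates.** With uniform 0-15 year follow-up, the ratio is 1.24 at 1% per year (section 3) and 1.23 at 1.4% per year (section 1). The relative error hardly depends on the rate.

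**Step 6. Treatment.** Set-up as in Step 3, assuming 32% are treated and treatment abolishes rupture risk:

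| Timing of treatment | Treated kept as event-free (Aim 1 list) | Treatment censors (general rule) |
|---|---|---|
| Constant rate over 5 years | 1.03-1.15 | 1.50-1.67 |
| All within year 1 | 0.88-0.98 | 1.29-1.43 |

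Entries are ratios to 3.61%. Which of the protocol's two rules applies decides both size and sign.

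**Step 7. Pilot follow-up.** 6,000/1,415 = 4.24 years, below the 5-year threshold. Tuning all exits to that mean gives ratios of about 1.7 to 1.85, depending on the shape of follow-up.

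**The case against.** Three arguments stand wholly or in part.

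First, a reader might infer that UK 5-year risk will be overstated, and for every score. The documents do not support that. The Aim 1 censoring list omits treatment, so treated patients may stay in as event-free and pull the estimate down. Step 6 shows that this can cancel or reverse the upward bias. The share and timing of treatment in this cohort are unknown, and section 5 (Aim 2 sensitivity analyses) expects a significant number to be treated for growth. What stands is that the selection component is upward. Cancellation by a second error would not make the rule sound.

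Second, a reader might take the roughly 80% overstatement from the pilot follow-up as the expected size. The protocol calls those years anticipated. It does not say what ended follow-up or how entry was spread, and the figure needs treatment to count as censoring. It is illustrative only.

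Third, the percentages per score may be meant to come from the time-to-event tools named just before them, and Hosmer-Lemeshow tests have survival versions that an analysis plan could specify. That is fair, so the named test is not in itself an error. But those tools would still be applied to the restricted set. Aim 3's Kaplan-Meier analysis of all patients offers a check on overall risk, not on risk per PHASES score.

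A further reading is that the rule selects on potential follow-up, dropping early ruptures among recent entrants too. That would be unbiased under independent censoring (3.61-3.63% in simulation), but the waiver for ruptures says otherwise.

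**Conclusion.** The defect is real and should be corrected before analysis. As written, Aim 1 selects patients on the outcome, and that selection biases the observed 5-year percentages upward. Under the Step 3 assumptions, the restriction alone turns 3.6% into about 4.4-4.9% and discards 27-42% of patients. The direction of this component follows from the text. Its size rests on an assumed follow-up distribution, constant hazard and independent censoring.

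The net error cannot be signed from the protocol, because its two censoring rules disagree on treatment. That contradiction is part of the finding. The protocol's expectation of no material overestimation does not hold for this component.

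**What to change.** In section 5, Aim 1:
1. Delete the 5-year completeness condition and compute the PHASES prediction for every eligible patient.
2. Reconcile the Aim 1 censoring list with the general last follow-up rule, so that treatment is handled the same way in both. Without this, removing the completeness condition leaves treated patients' event-free time in the estimate.
3. Estimate observed 5-year risk per PHASES score from all follow-up, by Kaplan-Meier or pseudo-values, or by cumulative incidence with death as a competing event. State which.
4. Assess calibration with the censoring-aware method already cited. Use a Hosmer-Lemeshow-type test only in a form that handles censoring.
5. Amend the statement that no significant overestimation is expected.

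The cost is a short rewrite of the Aim 1 text and one decision on treatment. No further data are needed, and the usable sample grows. Independent censoring remains an assumption to state, particularly if treatment censors.

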1 BACKGROUND

Intracranial aneurysms (IA) are common. Their prevalence is 3.2% in healthy people aged 50 (Vlak 2011). They occur with increasing frequency from the third decade onwards. They are usually asymptomatic and are detected incidentally on scans (usually MRI or CT) done for other reasons. Some can rupture and cause subarachnoid haemorrhage (SAH). The incidence of SAH is much lower at 9.1 per 100,000 person years (de Rooij 2007), reflecting a relatively low rate of IA rupture estimated at 1.4% per annum (Greving 2014).

Unruptured IAs (UIAs) can be treated prophylactically to prevent rupture with open microsurgery to apply a clip to occlude the aneurysm neck, or endovascularly to insert coils to fill the aneurysm sac. However, it is hard to justify treating all UIAs given these procedures carry a 5% or more risk of permanent morbidity or mortality, and very few rupture. It is therefore necessary to identify UIAs at high risk of future rupture for treatment.

An international attempt at a randomized controlled trial to address which patients benefit from treatment was stopped due to poor recruitment (just 80 patients consented to the study over 3 years out of a planned study size of 2000 (Raymond 2011)) and is unlikely to repeated. Therefore, treatment decisions are made based on what is known about the natural history of UIAs. The problem is that data on the natural history of UIAs is inadequate to inform major treatment decisions such as this.

Only one large multicentre prospective cohort has studied a population of UIAs applicable to the UK. The International Study of Unruptured Intracranial Aneurysms (ISUIA) was an international multicentre prospective cohort study which documented a strong relationship between aneurysm size (maximum diameter in any dimension at baseline) and SAH (Wiebers 2003). Five year SAH rates were 0% and 2.6% for IAs <7mm and 7-12mm respectively. ISUIA received extensive criticism both before (Ausman 2002), and after publication of results (Raymond 2008). A large number of patients were selected for treatment (58%), and of those selected for conservative management, many went on to have their UIA treated (32%) so that overall 72% were treated. This selection was not random, and the study population was not representative of all UIAs.

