A new risk prediction model for rupture will be developed using the total data set, including the additional possible risk factors. The Cox regression model will be used for risk of rupture. The absolute risks can be estimated at relevant time intervals, 2, 5 and 10 years. Numbers of missing values will be summarised for each factor. Multiple imputation will be used to replace missing values. Discrimination of the final model will be assessed with the Harrell's c-statistic. Internal validity will be assessed by bootstrap resampling.

Additionally, the following sensitivity analyses will be performed:

In view that a significant number of aneurysms are anticipated to have grown and subsequently treated on follow up, any cases noted to have undergone treatment for aneurysm growth will be included in a model predicting the risk of rupture or treatment for aneurysm growth. In view that it is anticipated that a number of unexplained deaths will be captured where it will not be possible to resolve if the cause was SAH or not, a model predicting aneurysm rupture or unexplained or unattended death (R 96 and 98) will be built.

Statistical analysis - Aim 3 - Long term rupture rates

It is anticipated that initially follow up times will range from months to 15 years. This will be insufficient to definitively answer what the long term risks posed by aneurysms are. However, a model will be built including a term for new diagnosis vs known diagnosis. This will establish if rupture rates are similar between patients with new and prior diagnoses.

All patients, including those who underwent aneurysm occlusion, will be included in time-to-event analysis which will cover the whole duration of available follow-up. This will include Kaplan-Meier and proportional hazards models for univariate and multivariate survival curve fitting. A cumulative Hazard plot will be used to assess if rupture risk is constant or varies with time from diagnosis.

Longer term, HES searches will be repeated periodically using unique HES identifiers generated by DARS at the first HES search. These searches will identify any late events of SAH due to aneurysm rupture and models will be built to predict true long-term risk.

Data management

Patient confidentiality

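### The general follow-up rule stops at aneurysm treatment, but the Aim 1 censoring list leaves treatment out and the Aim 3 sentence is ambiguous about time after occlusion

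*Protocol*

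**What the plan says.** Three statements in protocol section 5 bear on this.

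- **General rule** (under *other considerations* for the central HES and ONS data): the record closes at the HES query at the latest, and sooner if another listed event comes first. Treatment is one of those events: "or date of death, or the aneurysm was treated, whichever is earliest".
- **Aim 1** (*Statistical analysis - Aim 1 - PHASES validation*): time to censoring is "death or date of HES search or date unregistered from GP practice whichever is first". The list repeats the other three items and omits treatment. Its stated use is to make sure that patients without rupture have five years of follow-up. The PHASES 5-year risk is "to be calculated for all patients who are not censored before 5 years".
- **Aim 3** (*Statistical analysis - Aim 3 - Long term rupture rates*): "All patients, including those who underwent aneurysm occlusion, will be included in time-to-event analysis which will cover the whole duration of available follow-up". Neither censoring at occlusion nor a time-dependent treatment term is mentioned. A cumulative hazard plot is to show whether risk is constant.

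Treatment after inclusion is expected. The Aim 2 text says: "In view that a significant number of aneurysms are anticipated to have grown and subsequently treated on follow up". Aneurysms treated before entry are excluded (section 7.1.2), so only later treatment matters here. Date of and reason for treatment are collected.

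**The concern.** The study sets out to describe the natural history of untreated aneurysms. Person-time after occlusion is not natural history and is presumably at much lower rupture risk. If Aim 1 is run on its own list, that time enters as event-free follow-up and pulls down the observed 5-year risk, which is the quantity set against the PHASES prediction. PHASES could then appear to over-predict because aneurysms had been occluded. If Aim 3 is run over the full record, a growing share of occluded patients in the risk set would make a constant hazard appear to fall, and whether the hazard falls is the Aim 3 question.

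The protocol lists causes of underestimated risk to be corrected for in Aim 1: migration, miscoding, failed verification, and differences between local notes and HES. Treatment is not among them, so no later step removes the effect.

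**Working it through.** **1. Planning rate (section 7.2.1).** ISUIA recorded 51 ruptures in 1,692 patients over 4.1 years.

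- Rate r = 51 / (1,692 × 4.1) = 51 / 6,937.2 = 0.00735 per patient-year.
- Check against the plan: 60 × 1,692 / 51 = 1,990.6 patients and 1,990.6 × 4.1 = 8,161 patient-years. The protocol states 1,990 and 8,161, so the rate is the one it uses. The sample size is not in dispute.
- 5-year risk without treatment: R = 1 − exp(−5 × 0.00735) = 3.61%.

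**2. Assumptions not in the documents.** A share f is treated at time t (0.5 or 2.5 years), with no rupture afterwards, a constant hazard before, and average risk in the treated. The range for f is 10% to 32%. The upper end is the share of ISUIA's conservatively managed patients who were later treated (section 1), used only to set a range.

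**3. Aim 1 list as written (treatment does not censor).** Let q = 1 − exp(−rt), the risk before treatment: 0.367% at t = 0.5 and 1.821% at t = 2.5.

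Observed risk = (1 − f) × R + f × q.

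| f | t = 0.5 y | t = 2.5 y |
|---|---|---|
| 10% | 3.28% (9% too low) | 3.43% (5% too low) |
| 20% | 2.96% (18% too low) | 3.25% (10% too low) |
| 32% | 2.57% (29% too low) | 3.04% (16% too low) |

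Example: 0.68 × 3.609% + 0.32 × 0.367% = 2.57%. If a quarter of the hazard remains after occlusion, the understatement at f = 32% is 21% (t = 0.5) to 12% (t = 2.5).

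**4. Treatment added to the list, 5-year restriction kept.** Patients treated before 5 years without rupture now drop out, while those who ruptured before treatment stay in.

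Observed risk = [(1 − f) × R + f × q] / [(1 − f) + f × q].

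- f = 30%, t = 2.5: (0.7 × 0.03609 + 0.3 × 0.01821) / (0.7 + 0.3 × 0.01821) = 0.03073 / 0.70546 = 4.36%, 21% too high.
- f = 30%, t = 0.5: 3.76%, 4% too high.
- f = 32%: 3.77% (t = 0.5) to 4.43% (t = 2.5).

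The two ways of running Aim 1 therefore err in opposite directions.

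**5. Treatment censors and censored patients are kept.** With treatment unrelated to rupture risk, a Kaplan-Meier estimate targets R = 3.61%.

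**6. Aim 3.** If 32% are occluded at 6 months and stay in the risk set with no hazard, the average hazard goes from 0.735% to about 0.68 × 0.735% = 0.50% per year from that point, although the hazard of an untreated aneurysm has not changed.

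**The case against.** The strongest reply is that the general rule is framed for each patient and so governs every analysis. Occlusive treatment also appears under the data-collection headings for rupture and censoring events. On that view the Aim 1 parenthesis is an incomplete restatement, and the available follow-up in Aim 3 has already been cut at treatment, so Aim 3 merely keeps treated patients in the cohort up to occlusion.

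For Aim 3 this stands: the sentence can be read either way. A reader might infer that Aim 3 deliberately sets the general rule aside and counts occluded aneurysms as event-free. The text does not say so.

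For Aim 1 it stands only in part. The list is the specific rule for that analysis, is closed by its final clause, and repeats every general item except treatment. An analyst following it would be following the protocol.

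A reader might also carry over the ISUIA figure in the Background, "so that overall 72% were treated", and conclude that risk could be understated by well over half. The documents do not support that here. The protocol describes ISUIA as a cohort with high treatment rates, and section 8.4 says that most patients are advised against treatment. Shares of 50% or 72% fit poorly with that.

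Finally, treatment is probably related to rupture risk, so simple censoring may be informative. The protocol partly addresses this with the Aim 2 sensitivity model for rupture or treatment for growth. A further weighted analysis is a reasonable option, but its absence from the protocol is not an error.

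**Conclusion.** The Aim 1 censoring list is wrong as written: it contradicts the general rule and, if followed, biases the observed 5-year risk downward. The Aim 3 sentence is ambiguous and needs the same rule stated.

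Under the assumptions in step 2 of the working, the Aim 1 bias is about 5% to 29% in relative terms. The actual treatment share, timing and post-occlusion hazard in this cohort are unknown. The bias disappears if the general rule is applied and censored patients are kept. That clustering of treatment in high-risk strata would concentrate the bias there is plausible but was not calculated. Sample size is unaffected.

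**What to change.** 1. Add the date of occlusive treatment to the Aim 1 censoring list so that it matches the general rule.
2. In the same amendment, replace the restriction to patients not censored before 5 years. Estimate observed 5-year risk with a time-to-event method that keeps censored patients, for example Kaplan-Meier by PHASES score with 95% confidence intervals. Change 1 without change 2 would replace a downward bias with an upward one.
3. Reword Aim 3 so that treated patients contribute time up to occlusion and are censored there, with SAH after occlusion reported separately.
4. Optional: a weighted sensitivity analysis for informative censoring by treatment, alongside the model already planned under Aim 2.

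The cost is small: wording changes and a different estimator for the observed risk, using treatment dates that are already collected. The 5-year estimates will carry somewhat wider intervals, because time after occlusion no longer counts.

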7 SAMPLE AND RECRUITMENT

7.1 Eligibility Criteria

7.1.1 Inclusion criteria

- 1. Age 18 years or older.
- 2. Intracranial intradural unruptured aneurysm.
- 3. Confirmed on angiogram (CTA/MRA/DSA).

4. Diagnosis of UIA between January 2006-December 2020.

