7.2 Sampling

7.2.1 Size of sample

Sample Size

There are no accepted methods for power calculation for validation studies of prognostic models. Therefore, usually the rule of thumb to have ten events for every covariate tested is applied.

For Aim 1, 6 covariates will be tested suggesting at least 60 SAHs will need to be captured. ISUIA recorded 51 ruptures in 1692 patients over 4.1 years. Sixty events may therefore be expected in 1,990 patients with 8,161 years of follow up.

For Aim 2, 120 events will need to be observed to account for the 6 additional commonly occurring covariates which would be expected in 3,981 patients with 16,332 years of follow up.

For autosomal dominant polycystic kidney disease (ADPKD) which has a low incidence, larger numbers of patients will be needed. Ten events in ADPKD are expected in 1360 patient years of follow up assuming the risk of SAH is not elevated and similar to the general population. However, 16,332 years follow up would only yield 195 years in patients with ADPKD (based on a population study which found 53/4436 IAs had ADPKD (Nurmonen 2017) and consistent with pilot data where 11/1025 cases examined to date had ADPKD). Therefore 113,905 years of follow up would be required to capture 10 ruptures amongst 1,340 years follow up in ADPKD patients. This would equate to 22,781 patients with 5 years of follow up (or applying the slightly looser rule of 5 events per prognostic factor this would require 56,952 years of follow up with 11,391 patients).

In a local pilot 1,415 cases were identified over 14 years in a population of 3 million with an anticipated 6,000 years of follow up. Extrapolating to England, Wales and Scotland 31,130 patients with 132,200 years follow up are available - well in excess of the target of 8,161 to validate PHASES in the general population, as well as the 16,332 to test the additional variables, but only just sufficient to answer the role of rarer predictors such as ADPKD. For reference PHASES was based on 29,166 years of patient follow up. Therefore, all cases that can be identified in England and Wales will be sought up to a maximum of 22,781.

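### The correction for unrecorded emigration subtracts observed emigration from a national average that is not matched to the cohort, so the Aim 1 risks carry an error equal to the gap between the two populations' emigration rates

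*Protocol*

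**What the plan says.** Section 5, Statistical analysis – Aim 1, lists reasons why rupture risk may be underestimated and promises that "The magnitude of these will be estimated and corrected for". For emigration, departures noted at baseline or seen as GP de-registration become censoring events. The protocol expects some patients to leave without de-registering. To cover them, the observed emigration rate "will be subtracted from average national migration figures and this applied to the data".

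No age, sex or calendar-year matching of the national figure is mentioned. For errors in the other direction, the same section states that, because SAH events are verified in the notes, "it is not expected that there will be any significant overestimation and consequently correction". A last step compares corrected events with SAH events in local notes, with "the total risk estimates adjusted for any differences between these to give final 5 year risk estimates".

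The cohort is defined in Section 7.1.1 ("Age 18 years or older", with an angiographically confirmed unruptured aneurysm) and is found through neurosurgical units (Section 7.3.1). Section 1 says of aneurysms: "They occur with increasing frequency from the third decade onwards".

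**The concern.** Unrecorded emigration in this cohort is the cohort's true emigration rate minus what was recorded. The plan replaces the first term with a national average. Any difference between the two populations is then counted as missed departures, and person-time is corrected for people who may never have left.

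The protocol's reassurance about overestimation rests on verifying SAH events. That protects the count of events. It does nothing for an error in the time at risk.

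The corrected figures are the 5-year risks that Aim 1, a primary aim, sets against the PHASES predictions. A benchmark error moves the observed risks for a reason unrelated to PHASES, and a larger cohort does not reduce it.

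**Working it through.** **Reproducing the protocol's planning figures (Section 7.2.1).** "ISUIA recorded 51 ruptures in 1692 patients over 4.1 years".
- Rate: 51 / (1692 × 4.1) = 51 / 6937.2 = 0.735% per year.
- Aim 1 target: 60 / (51/1692) = 1,990.6 patients and 60 / 0.0073517 = 8,161 years. Both match the stated 1,990 and 8,161.
- At the largest target, 113,905 years × 0.0073517 = 837 events.
- Implied 5-year risk at a constant rate: 1 − exp(−0.0073517 × 5) = 3.61%.

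**The error in the rule.** Let N be the national rate, C the cohort's true rate and O the cohort's observed rate.
- Correct hidden emigration: C − O.
- The plan's hidden emigration: N − O.
- Error: (N − O) − (C − O) = N − C.

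O cancels, so the error does not depend on how complete the de-registration data are. With complete recording (O = C) the right correction is zero and the plan still applies N − C.

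**Size at 5 years.** The documents give no emigration rate, so d = N − C is an assumed range. The protocol does not say how the difference is applied; I assume it removes person-time. Over t years the share of person-time kept is (1 − exp(−dt)) / (dt), so the rate is multiplied by dt / (1 − exp(−dt)), roughly 1 + dt/2.

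| Assumed d per year | Multiplier at t = 5 | 5-year risk (true value 3.61%) |
|---|---|---|
| 0.2% | 0.010 / 0.00995 = 1.005 | 3.63% |
| 0.5% | 0.025 / 0.02469 = 1.013 | 3.65% |
| 0.7% | 0.035 / 0.03439 = 1.018 | 3.67% |

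The absolute shift is 0.02 to 0.06 percentage points. If the cohort emigrates more than average, the sign reverses: d = −0.2% gives a multiplier of 0.995 and a risk of 3.59%; d = −0.7% gives 0.983 and 3.55%. With d = 0 the true 3.61% is returned.

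**Against sampling error.** The relative 95% half-width is 1.96/√837 = 6.8% at 837 events and 1.96/√60 = 25.3% at 60. For d = 0.7%, the shift in z at 837 events is ln(1.0176) × √837 = 0.50, so a nominal 5% test of overall calibration would reject a correct prediction about 8.0% of the time. For d = 0.2% and 0.5% the figures are 5.2% and 6.5%. At 60 events the worst case shifts z by 0.0174 × √60 = 0.14, giving about 5.2%.

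**Compared with making no correction.** Assume a national rate of 0.5% per year, a cohort rate one quarter of that, and half of departures recorded. The uncorrected rate is then 0.16% too low and the plan's corrected rate 0.93% too high. The correction adds more error than it removes whenever N − C exceeds C − O.

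**The case against.** **Direction.** A reader might infer that UK rupture risk is certain to be pushed upward because the cohort is older and emigrates less. The documents do not support that. They give no cohort age distribution and no emigration rate; the age floor of 18 and the remark on rising frequency are only indirect. The direction is conditional.

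**Level of detail.** The choice of table and its standardisation could be left to the SAP, which is not shown, and the wording does not expressly rule out age-specific figures. This stands in part. But the protocol does more than stay silent: it states the subtraction and describes its benchmark as an average.

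**Migration or emigration.** A reader might take the benchmark to be net migration, which would not measure departures at all. The surrounding text is about departures, so that reading is strained. The wording is only worth tightening.

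**Longer horizons.** The same formula gives larger errors at 10 or 15 years. The protocol states this correction only for Aim 1 and its 5-year risks, and the Aim 2 and Aim 3 analyses do not invoke it, so those figures should not be held against the plan.

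**Size.** The 5-year effect is small, and 837 events would need the maximum cohort, which was sized for polycystic kidney disease. The plan also compares risks by PHASES score, where each group has fewer events and wider intervals. This stands and sets the severity.

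**The later comparison with local notes.** It may remove or alter part of the error. It is not a reliable guard: Section 3 says ruptures cannot be identified from neurosciences records, because many patients are admitted elsewhere.

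**Conclusion.** The point holds as a mismatched benchmark. The error equals the national average minus the cohort's true emigration rate and does not depend on how well departures are recorded. Under an assumed gap of 0.2 to 0.7% per year, a constant rupture rate and removal of person-time, the bias is about 0.5 to 1.8% relative at 5 years, upward if the cohort emigrates less than average and downward if it emigrates more. It is well inside sampling error at any planned cohort size, but more patients will not remove it. A reader might infer that the comparison would wrongly show PHASES to underestimate UK risk; neither the size nor the unproven direction supports that. Minor severity.

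**What to change.** In Section 5, Aim 1 analysis:

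- Replace the average national migration figure with published gross emigration (outflow) rates by age, sex and calendar year, and name the source.
- Apply them to the cohort's own person-years to obtain expected emigrants. Subtract the observed emigrants and apply the remaining difference to person-time.
- If observed emigrants meet or exceed expected, make no correction and say so in the report. Recorded departures are already censored, so an excess leaves nothing to correct.
- Report the 5-year risks with and without this correction, so that the PHASES comparison can be judged without it.

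The cost is a change of wording and one standardisation step. Age, gender and date of inclusion are already collected, and no new patients or data collection are needed. The small downside is that general-population rates still do not reflect this cohort's health, so some uncertainty in the correction remains; showing the uncorrected risks makes that visible.
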